Early Help practitioners (n) n = 12	Framework analysis based on Theoretical Domains Framework and fidelity checklist.	RQ2, RQ3	Beginning these interviews in the pilot phase will surface any problems that need rectifying for the efficacy phase.
Gateway Leads n = 3	Framework analysis based on Theoretical Domains Framework and inductive coding regarding organisational issues.	RQ3	Conducting these interviews in the pilot phase will inform any changes needed to the referral pathways for the efficacy.

Cost data reporting and collecting

Cost data will be collected from the delivery partner, as it will refer solely to the delivery of MBT-PP, rather than TAU, in line with YEF guidelines. Cost data will be gathered every 6 months and will capture actual, rather than estimated, spend.

Cost data will be gathered using therapist diaries and salary information from the delivery partner. Because the number of therapists delivering MBT-PP is relatively small (n=12), we will aim for cost data on the entire workforce. Because the 12 MBT-PP therapists will be

delivering the intervention in 3 different LAs, but all online from one central organisation (the delivery partner) gathering these data from the perspective of the delivery partner ought to be straightforward. Cost data will also be gathered on therapist training, supervision, and overheads such as ITC requirements.

Ethics and registration

The process for obtaining ethical approval is via Sheffield Hallam University (SHU) which has established research ethics policies and procedures aligned with legal requirements and research societies' standards of good practice (<https://www.shu.ac.uk/research/quality/ethics-and-integrity>). The project team will follow these procedures, including operating to standardised protocols concerning anonymity, confidentiality, informed consent, rights to withdraw, and secure data privacy.

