Please see risk register in Table 6.

Evaluation of Tavistock Relationships MBT-PP to improve child outcomes by reducing inter-parental conflict: a pragmatic efficacy randomised controlled trial with internal pilot

Evaluation protocol

Evaluating institution: Sheffield Hallam University

Principal investigator(s): [name]

Table 6. Risk register

Potential Risk Identification	Initial potential risk status			Preventative measures	Reducing the impact	Revised risk status		
	Likelihood	Impact	Risk			Revised Likelihood	Revised Impact	Revised Risk
Project specific risks								
Low recruitment	medium	medium	medium	Gateway Lead posts in each of the 3 LAs will oversee recruitment. Relationship building and significant project promotion activity by Tavistock Relationships with the LA staff will raise the profile of the project. In the event of low recruitment, we will explore the option of expanding to additional LAs.	Trial design can be adapted as necessary.	low	low	low
Attrition	medium	medium	medium	Encouraging compliance through strong rapport, advance notice and clear communication. Full	We use a dedicated project management/administrative support team to ensure a close	low	low	low

				investigation of causes of attrition in the in the pilot stage. Incentives for each questionnaire completed and an additional bonus incentive for completing all questionnaires.	positive working relationship with all stakeholders in the trial. Any attrition will be recorded using a consort flow diagram and taken into account at the analysis stage.			
Deliverer staffing difficulties	medium	high	medium	The deliverer should ensure that cover is available in the event of staff absence or departure	Each therapist could have a designated cover to pass clients onto in the event of illness or departure. Such staffing changes will be recorded and taken into account in the analysis as changes in therapeutic relationships may affect outcomes.	low	medium	low
Generic risks								
Covid 19 related disruption	High	medium	high	Team will closely monitor any evolving pandemic-related scenarios. Intervention delivery is all online so should not be affected. All staff are able to work remotely.	Team are used to working flexibly and responsively to changes to projects, timescales and participant needs. In consultation with YEF, team able to put forward revised evaluation plans based on various future scenarios	low	low	low

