	Level 3 (cluster)	0.01 to 0.15	0.27
Alpha		0.05	0.05
Power		0.80	0.80
One-sided or two-sided?		Two	Two
Average cluster size		2 CYP per family	1.4 CYP per family
Number of clusters	Intervention	175	125
	Control	175	125
	Total	350	250
Number of participants (CYP)	Intervention	350	175
	Control	350	175
	Total	700	350

The power analyses published in the protocol included key parameters for which no empirical estimates could be obtained. Specifically, these were covariate explanatory power (from the baseline mothers SDQ measure) at CYP and family levels and the family level ICC for the mothers SDQ measure at outcome. The protocol used relatively wide ranges of values for CYP and family level explanatory power (between 0.25 and 0.49) and ICC (0.01 to 0.15).

As specified in the protocol, analyses of data from the internal pilot provides empirical point estimates for these parameters for use in the updated power analyses presented here. At the time of writing (August 2024), a total of 43 families (21 allocated to MBT and 22 to TAU) with 61 CYP (30 MBT, 31 TAU) had complete baseline/T1 and outcome (T2, post intervention) mothers SDQ. Analyses of these 61 CYP in 43 families has been used to provide empirical estimates for ICC and explanatory power at the family and CYP levels.

The power analyses were undertaken using equation 1.0 below and checked using the PowerUp! software (Dong & Maynard, 2013, sheet CRA2_2r).

$$[1.0] \quad MDES_{2LCRT} \sim M_{J-m-2} \sqrt{\frac{1}{P(1-P)}} \sqrt{\frac{ICC(1-R_{Fam}^2)}{J} + \frac{(1-ICC)(1-R_{CYP}^2)}{nJ}}$$

For a 2-level CRT design, the MDES is influenced by (estimates updated from analyses of pilot data):

- n=number of CYP per family = **1.4** (updated from 2.0 in protocol).
- J = number of families (**90** at pilot, allowed to vary up to **400** see below).
- P = proportion of families allocated to intervention group (= **0.50**).
- m= number of (level 2) covariates used (which will include: group membership, family-level pre-test, 4 (dummy) variables used for minimisation ~ **6** variables).
- M_{J-m-2} is the group effect multiplier value of the t-distribution for a 2-tailed test with alpha=0.05 & beta=0.80.
- ICC is the family level ICC = **0.27** (updated from 0.01 to 0.15 in protocol). This is the proportion of variance of the outcome at level 2 (between-family variance).

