The updated power analyses presented here illustrate that, even with fewer CYP per family than initially estimated, a smaller sample of families is likely to be sufficient sensitivity to detect an MDES of 0.20 sds or higher than was estimated at protocol. With 250 families (and 350 CYP), the MDES estimate is 0.17 sds. With an attrition rate of 10%, assuming attrition was random, the indicative MDES estimate is 0.18 sds. With an attrition rate of 20%, assuming attrition was random, the indicative MDES estimate is 0.19 sds.

Therefore, following the updated power analysis, the recommended sample size for the evaluation of the Tavistock MBT-PP programme is reduced from 350 families (700 CYP) to be 250 families (350 CYP).

Analysis

Research questions were operationalised as follows:

RQ1 Does MBT-PP (compared to TAU) delivered to parents experiencing IPC lead to lower externalising and internalising behaviours in children aged 8-14 (as measured by the SDQ total 'difficulties' scale)?

This splits into two separate RQs (SDQ total difficulties for mothers and for fathers).

RQ1a Does MBT-PP (compared to TAU) delivered to parents experiencing IPC lead to lower externalising and internalising behaviours in children aged 8-14 as measured by the mother's SDQ total 'difficulties' scale? – PRIMARY OUTCOME RQ1

RQ1b Does MBT-PP (compared to TAU) delivered to parents experiencing IPC lead to lower externalising and internalising behaviours in children aged 8-14 as measured by the father's SDQ total 'difficulties' scale? – SECONDARY OUTCOME RQ1

RQs 2-8 inclusive also all examine secondary outcomes, and, apart from those where the outcome variable comes from CYP rather than parents (RQ2 regarding child wellbeing and RQ4 regarding child perception of IPC), they split into a) maternal report and b) paternal report, as per RQ1.

RQ2 Does MBT-PP (compared to TAU) delivered to parents experiencing IPC lead to higher wellbeing in children aged 8-14 (as measured by the Stirling Children's Well-being Scale)?

RQ3 Does MBT-PP (compared to TAU) delivered to parents experiencing IPC lead to lower IPC reported by parents (as measured by the O-Leary-Porter Scale)?

RQ3a Does MBT-PP (compared to TAU) delivered to parents experiencing IPC lead to lower IPC reported by mothers (as measured by the O-Leary-Porter Scale)?

RQ3b Does MBT-PP (compared to TAU) delivered to parents experiencing IPC lead to lower IPC reported by fathers (as measured by the O-Leary-Porter Scale)?

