- $\beta_{4..7}$ are the coefficient estimates for the four family-level dummy variables.

² This because centring the CYP level scores around their cluster (family) mean is an orthogonal transformation, CYP scores are placed relative to their family mean and so will not share any variance ($r = 0$).

- ϑ'_j and ε'_{ij} are random effects that remain at the school and pupil levels and are assumed to be distributed normally in the population with zero means, variances σ_c^2 and τ_c^2 respectively, and for these variances to be conditionally uncorrelated.

The estimate of impact will be standardised as an effect size by dividing by the standard deviation obtained from the variance partition estimates for the empty/null model described in equation 2.1:

$$[2.1] \quad Y_{ij} = \beta_0 + \vartheta_j + \varepsilon_{ij}$$

Where:

- β_0 is the constant term for the empty model and represent the mean mothers reported SDQ-TD for CYP at T2 (16 weeks following minimisation).
- ϑ_j and ε_{ij} are random effects at the school and pupil levels and are assumed to be distributed normally in the population with zero means, variances σ^2 and τ^2 respectively.

Table 5 summarises the ITT analysis for the mothers SDQ-TD primary outcome described in equation 2.0.

Table 5. Example analysis model for mothers SDQ-TD primary outcome (RQ1a)

Analysis and Sample	Level 1 (CYP) Covariates	Level 2 (Family) Covariates	Outcome Variable
Null/Empty model			CYP level mothers SDQ-TD (raw) score at T2 (16 weeks following minimisation)
Final Model	Mothers SDQ-TD score at T1/baseline (Centred around family mean)	Mean mothers SDQ-TD score at T1/baseline (Centred around grand mean) Group membership (MBT or TAU) Four Minimisation Dummy Variables: CYP ages (2); parental ethnicity (1), relationship status (1);	CYP level mothers SDQ-TD (raw) score at T2 (16 weeks following minimisation)

The empty model is described by equation 2.1 and the final model by equation 2.0. The impact of the MBT-PP programme (compared with TAU) amongst parents experiencing IPC on

mothers SDQ-TD scores will be estimated using the coefficient for the group membership family-level covariate included in the final model (β_1 in equation 2.0). Impact will be standardised into an effect size by dividing the β_1 coefficient shown by the unconditional standard deviation from the null/empty model described in equation 6.0 below.

Secondary outcome analysis

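### The primary model and the 0.17 SD MDES assume zero therapist variance, although 12 therapists deliver MBT-PP to up to 125 allocated families

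*SAP*

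**What the plan says.** **Model.** Under SAP Primary outcome analysis, the random terms of equation 2.0 "are random effects that remain at the school and pupil levels and are assumed to be distributed normally in the population with zero means". The subscripts, Table 5 and Presentation of outcomes show that the levels meant are family and CYP. Under Compliance, the CACE standard errors are adjusted for children within families only. Neither document has a therapist term, a therapist ICC or a therapist sensitivity analysis.

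**Power.** Equation 1.0 (SAP Sample size calculations) uses the same two levels: "With 250 families (and 350 CYP), the MDES estimate is 0.17 sds". That result supports the reduction from 350 to 250 families against a goal of 0.20 SD. The SAP's Analysis section then treats an observed difference of 0.17 SD or more as evidence of impact.

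**Delivery.** The protocol's cost section says: "Because the number of therapists delivering MBT-PP is relatively small (n=12"; Therapist interviews gives the same number. On cover for absent or departing therapists, the risk register (protocol Table 6) says: "Such staffing changes will be recorded and taken into account in the analysis as changes in therapeutic relationships may affect outcomes". The SAP contains nothing that does this.

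**The concern.** Families seen by the same therapist may have correlated outcomes. A family random effect cannot absorb this, because the correlation lies between families. With 125 families over 12 therapists, even a modest therapist variance enters the MBT-PP arm mean divided by 12, not by 125. The two-level model would then understate the SE of the treatment effect. The primary test would reject too often, and the MDES behind the smaller sample would be too low. A borderline positive result would be open to challenge, and a therapist term added after unblinding would be post hoc.

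**Working it through.** **Inputs.** From SAP Table 2 and the list under equation 1.0: 250 families, half per arm (125 each); 1.4 CYP per family; family ICC 0.27; R² 0.75 (CYP) and 0.61 (family); m = 6; two-sided alpha 0.05; power 0.80. From the protocol: 12 therapists. Assumed, because the documents give no value: therapist ICC c, as a share of residual family-mean variance.

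**1. The plan's own figure** (total variance set to 1).
- Residual variance of a family mean: v = 0.27 × 0.39 + 0.73 × 0.25 / 1.4 = 0.1053 + 0.1304 = 0.2357.
- SE = √(4 × 0.2357 / 250) = 0.0614.
- The multiplier on 250 − 6 − 2 = 242 df is 2.813, so MDES = 2.813 × 0.0614 = 0.173. The SAP states 0.17.
- With 200 families (20% attrition) the same formula gives 0.193. The SAP states 0.19.

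The SAP's arithmetic is right for a design with no therapist variance.

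**2. Therapists nested in the MBT-PP arm.** Take the therapist variance cv out of v, with even caseloads, all allocated families treated and no clustering in TAU.
- Variance of the MBT-PP mean = cv/12 + (1 − c)v/125; of the TAU mean = v/125.
- Design effect in the MBT-PP arm = 1 + (125/12 − 1)c = 1 + 9.42c.
- SE ratio to the two-level model = √(1 + 4.71c).
- Type I error of the planned test = 2 × [1 − Φ(1.96 / SE ratio)].
- MDES = multiplier × 0.0614 × SE ratio, with Satterthwaite df combining 11 df (MBT-PP) and 121 df (TAU).

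For c = 5%: the MBT-PP variance is 0.000982 + 0.001791 = 0.002773 and the TAU variance 0.001885. The SE is √0.004658 = 0.0683, a ratio of 1.11. On 29.8 df the multiplier is 2.897, so the MDES is 0.198.

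| c (assumed) | as share of total variance (c × v) | design effect | SE ratio | type I error | df | MDES (SD) |
|---|---|---|---|---|---|---|
| 1% | 0.24% | 1.09 | 1.02 | 5.5% | 37.5 | 0.181 |
| 2% | 0.47% | 1.19 | 1.05 | 6.1% | 35.0 | 0.185 |
| 5% | 1.18% | 1.47 | 1.11 | 7.8% | 29.8 | 0.198 |
| 10% | 2.36% | 1.94 | 1.21 | 10.6% | 24.7 | 0.217 |

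The MDES passes 0.20 SD at c of about 5.6%. Part of the rise is the loss of df: with the 242-df multiplier the 1%, 5% and 10% values would be 0.177, 0.192 and 0.210.

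**3. Check of the type I formula.** Simulation of 20,000 trials per value gave 4.9% with no therapist variance. With therapist variance at 1% and 2% of total variance (4.2% and 8.5% of v), it gave 7.6% and 10.1%, against 7.4% and 9.8% from the formula.

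**4. 20% attrition.** With 100 families per arm (8.3 per therapist; 11 and 96 df), c = 1% gives 0.201 and c = 2% gives 0.205, about 0.20 SD against the stated 0.19. With 192 df they would be 0.197 and 0.200, so much of this shift is the df.

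**Scale.** The result depends on how the ICC is expressed. A therapist share of 1% of total variance is 4.2% of v and gives an MDES of 0.195.

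**The case against.** The harm is conditional, and the documents give reasons to expect a small therapist variance. The therapy is manualised, therapists have fortnightly group supervision meant to hold them to the manual, there is no direct work with children, and the outcome is a mother's report on her child. At 1-2% the consequences are minor. This stands: it limits the size of the point but does not show that the variance is zero.

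The 12 therapists are the provider's whole MBT-PP workforce, so for inference to those therapists the two-level SE is defensible. This also stands, and it is why the therapist term belongs in a sensitivity analysis. The protocol's question on delivery at scale (implementation RQ3) does look beyond these 12.

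TAU too is delivered by people: local authority staff guide parents through the digital resources. Their number and caseloads are not given, so clustering in one arm only is an assumption. Practitioner clustering in TAU would add variance and would not rescue the two-level SE.

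The two counts come from different plans. Twelve therapists were named when 175 MBT-PP families were expected; 125 is the SAP's allocated number. Some allocated families will be found unsuitable at assessment yet stay in the ITT analysis, which dilutes any therapist effect. Uneven caseloads would work the other way.

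A reader might infer from the risk register that the protocol promised to model therapists. It did not: the entry concerns staffing changes and says only that they may affect outcomes.

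**Conclusion.** The omission is real: the primary SE, its p-value and the 0.17 SD MDES all rest on an unstated assumption of zero therapist variance. Under the assumptions in the working, the cost ranges from negligible (type I error 5.5%, MDES 0.18 SD at an ICC of 1%) to material (10.6%, 0.22 SD at 10%). The 0.20 SD goal is missed above about 5.6% with no attrition, and is reached at 1-2% under the SAP's 20% attrition scenario.

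Two stronger readings are tempting: that the primary p-value is anti-conservative as a matter of fact, and that the reduction to 250 families is wrong. The documents support neither, because both need a therapist variance that they do not give.

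**What to change.** - **Data.** Ask the delivery partner for the therapist first allocated to each MBT-PP family, and record the TAU practitioner if known. The protocol's list of administrative data has sessions per family and per therapist but not this link. Appendix A (criterion 6) implies that it exists, since families are allocated to a therapist. Using first allocation settles how cover therapists are handled.
- **Analysis.** Pre-specify a sensitivity analysis of the primary outcome that adds a therapist random coefficient on T_j, with REML and Satterthwaite or Kenward-Roger df. Families never allocated a therapist are their own clusters. Report the therapist ICC. If the model does not converge, report results with the therapist variance fixed at 1%, 5% and 10% of residual family-mean variance.
- **Decision rule.** State that the p-value from equation 2.0 remains primary, and that a significant result which does not survive the therapist-adjusted analysis will be described as not robust to therapist clustering.
- **Power.** Present 0.17 SD as assuming zero therapist variance, next to the range above.
- **Wording.** Change the random-effect labels from school and pupil to family and CYP.

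The cost is SAP wording and one data request, within the mixed-model framework already planned. The downside is a slightly wider interval in the sensitivity analysis and a less favourable MDES.

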This trial is running in 3 local authorities, Bristol, Dorset, and Bournemouth, Christchurch, and Poole (BCP). In each local authority, this evaluation funds a 'Gateway Lead' post. Postholders are staff with experience of working with CYP and families and have backgrounds in primary teaching and family support.

Gateway Leads have created referral pathways into the project and promoted awareness of the project in schools and other relevant local authority staff. When referred, families are screened for eligibility against exclusion and inclusion criteria and taken through the consent

process. Once consent is obtained, families complete baseline assessments, and are subsequently randomly allocated to receive either MBT-PP or TAU. Allocation is conducted by the evaluator according to a minimisation protocol to ensure a balanced sample. Families then undergo their allocated treatment. Once treatment has completed, families complete post-intervention assessments. Follow up assessments are completed 3 months later.

The primary outcome variable for this trial is the ‘Total Difficulties’ (TD) subscale of the Strengths and Difficulties Questionnaire (SDQ; Goodman, 1997) obtained from the mothers’ post-intervention assessment, reporting on the CYP. As such, analyses will focus on comparing mothers’ post-intervention TD scores between MBT-PP and TAU. Secondary outcome variables are fathers’ post-intervention TD score; and child psychological well-being (as measured by the Stirling Children’s Well-being Scale, Liddle & Carter, 2015).

The trial is also assessing proposed mechanisms of action, by assessing: parent report IPC (as measured by the O’Leary-Porter Scale, OPS, Porter & O’Leary, 1980, adapted as described in the protocol); child perception of IPC (as measured by the Perceptions of Interparental Conflict-Intensity/Frequency Scale, PIC-I/F, Kline, Wood & Moore, 2003); parent anger (as measured by the Dimensions of Anger Reactions-Revised, DAR-R, Nederlof et al., 2009); parent mentalising capacity (as measured by the Parental Reflective Function Questionnaire, PRFQ, Luyten et al., 2009); parenting style (as measured by the Parenting Scale Short Form, PS-8, Kliem et al., 2019); and, for separated parents only, parent emotional adaptation to separation (as measured by the Emotional Adaptation to Relationship Dissolution Assessment, EARDA, Millings et al., 2020).

Table 1. Trial design overview

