will not result in different estimates of coefficients (and hence impact) compared with using raw scores at CYP level and aggregated mean scores at the family/parent level but brings other statistical advantages. Hedges & Hedberg (2007) note that using cluster (mean) centring results in more stable estimates of variance components when covariate values vary substantially across clusters. Centring also ensures no issues of multicollinearity because the correlation between the cluster- and CYP-level centred variables will be zero². Finally, centring results in a more realistic coefficient estimate for the constant term because this relates to a mean score (rather than a score of zero) on the T1 mothers SDQ-TD score.

Primary outcome analysis

A multilevel linear regression model will be used to estimate the impact of the Tavistock MBT-PP intervention, on mothers-reported SDQ total difficulties (SDQ-TD) score for their children. Whilst mothers-reported SDQ -TD score represents the single primary outcome for the impact evaluation, fathers SDQ-TD score will also be analysed as a secondary outcome (see below).

For the analysis of the primary outcome, an estimate of impact will be obtained from a hierarchical (multilevel) linear model described in equation 2.0:

$$[2.0] \quad Y_{ij} = \beta_0 + \beta_1 T_j + \beta_2 (X_{ij} - \bar{X}_j) + \beta_3 (\bar{X}_j - \bar{X}) + \beta_{4..7} [MIN DUM]_j + \vartheta_j' + \varepsilon_{ij}'$$

Where:

- Y_{ij} is the mothers reported SDQ-TD for CYP i in family j at T2 (16 weeks following minimisation).
- T_j is the family-level group identifier which will take the value 1 (=MBT) or zero (=TAU)
- β_1 is the coefficient that estimates the difference between the MBT and TAU groups adjusted for baseline scores and minimisation variables; i.e. $\beta_1 = (MBT - TAU)_{adjusted}$. The β_1 coefficient will be used to estimate the AITT (see below).
- X_{ij} is the mothers reported SDQ-TD for CYP i in family j at T1/baseline centred around \bar{X}_j , the family-level mean (i.e. $(X_{ij} - \bar{X}_j)$)
- \bar{X} is the family-level grand mean mothers reported SDQ-TD score used to centre \bar{X}_j , the family-level mean (i.e. $\bar{X}_j - \bar{X}$)
- $[MIN DUM]_j$ is the collection of four family-level dummy variables used in the minimisation; ages of CYP in family (two variables); whether one parent was not White British (one variable) and relationship status (one variable).

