Table 7. Example (relationship status) subgroup analysis for mothers SDQ-TD primary outcome

Analysis and Sample	Level 1 (CYP) Covariates	Level 2 (Family) Covariates	Outcome Variable
Main Effects Final Impact Model (Complete ITT Sample)	Mothers SDQ-TD score at T1/baseline (Centred around family mean)	Mean mothers SDQ-TD score at T1/baseline (Centred around grand mean) Group membership (MBT or TAU) Four Minimisation Variables: CYP ages (2); parental ethnicity (1), relationship status (1);	CYP level mothers SDQ-TD (raw) score at T2 (16 weeks following minimisation)
Interaction Model (Complete ITT Sample)	Mothers SDQ-TD score at T1/baseline (Centred around family mean)	Mean mothers SDQ-TD score at T1/baseline (Centred around grand mean) Group membership (MBT or TAU) Four Minimisation Variables: CYP ages (2), parental ethnicity (1), relationship status (1) Interaction: Group Membership*relationship status	CYP level mothers SDQ-TD (raw) score at T2 (16 weeks following minimisation)
Assuming a statistically significant interaction term...			
Null/Empty Models Two Subsamples: CYP in intact families AND			CYP level mothers SDQ-TD (raw) score at T2 (16 weeks following minimisation)

CYP in separated families.			
Subgroup Impact Models Two Subsamples: CYP in intact families AND CYP in separated families.	Mothers SDQ-TD score at T1/baseline (Centred around family mean)	Mean mothers SDQ-TD score at T1/baseline (Centred around grand mean) Group membership (MBT or TAU) Three Remaining Minimisation Variables: CYP ages (2), parental ethnicity (1).	CYP level mothers SDQ-TD (raw) score at T2 (16 weeks following minimisation)

Further analyses

Sensitivity analyses will be undertaken to examine two things; first to examine whether time (between baseline and outcome data collection) influenced the outcome and estimated impact; second, to examine impact at the pilot and stage 2 evaluations (which are combined to form this efficacy study with an internal pilot).

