To examine the influence of time we will first statistically summarise the time (in weeks⁵) between baseline (T1) and outcome (T2) and the bivariate relationship between time and the mothers SDQ TD outcome at T2 for the MBT and TAU groups. Following this we will take a similar approach to the CYP age subsample analysis and introduce time (in weeks) as a CYP-level main effects term (centred around the CYP level mean; CYP_CWeeks_{ij}) and as an interaction with the family-level group identifier ($T_j \times CYP_CWeeks_{ij}$) in a hierarchical linear model, as described in equation 5.0:

$$[5.0] Y_{ij} = \beta_0 + \beta_1 T_j + \beta_2 (X_{ij} - \bar{X}_j) + \beta_3 (\bar{X}_j - \bar{X}) + \beta_4 CYP_CWeeks_{ij} + \beta_5 T_j \times CYP_CWeeks_{ij} + \beta_{6..9} [MIN DUM]_j + \vartheta_j + \varepsilon_{ij}$$

If the β_5 main effects term for time is statistically significant, this would indicate that mothers SDQ TD at T2 was associated with the number of weeks between baseline (T1) and outcome (T2) measures. This would not necessarily indicate a problem with the estimate of impact from the ITT analysis but would provide useful context. However, if the β_5 interaction coefficient is observed to be statistically significant, this would raise a question on the validity

⁵ Measured in days but included as decimalised 'weeks' with the assumption of a mean of 16.0 weeks.

of the ITT estimate (because the interaction term would suggest that this estimate depended on the amount of time between T1 and T2). If the β_5 interaction coefficient is observed to be statistically significant, the sign would indicate whether increased time (weeks between T1 and T2) resulted in higher (positive) or lower (negative) estimates of impact. Follow-on analyses would be undertaken on subsamples of participants determined by time. This might be three subsamples (below mean, mean, above mean) but is dependent on subsample size and will be determined following an examination of the data.

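### The SAP lets an arm-by-weeks interaction, based on an interval measured after randomisation, cast doubt on the ITT estimate and trigger data-driven time subsamples; a constant effect can produce that signal

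*SAP*

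**What the plan says.** The SAP (Further analyses) plans a sensitivity analysis, "first to examine whether time (between baseline and outcome data collection) influenced the outcome and estimated impact". Equation 5.0 adds centred T1-T2 weeks as a main effect and as an interaction with arm. Footnote 5 has the interval measured in days and entered as decimal weeks, "with the assumption of a mean of 16.0 weeks". No SD, distribution or acceptable window is given for either arm.

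The decision rule follows. If the "interaction coefficient is observed to be statistically significant, this would raise a question on the validity" of the ITT estimate, "because the interaction term would suggest that this estimate depended on the amount of time between T1 and T2". The next step is: "Follow-on analyses would be undertaken on subsamples of participants determined by time". Three groups around the mean are suggested, but the choice "will be determined following an examination of the data".

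The documents describe T2 timing in two ways. The SAP's Design overview says: "Once treatment has completed, families complete post-intervention assessments". The Primary outcome analysis section defines the outcome as the score "at T2 (16 weeks following minimisation". The protocol (Evaluation Design) treats 16 weeks and completion of MBT-PP as the same moment. However, its description of the intervention allows weekly or fortnightly sessions with some flexibility, and Appendix A (criterion 8) monitors discharge before the treatment protocol is complete.

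**The concern.** T1-T2 weeks is not a baseline characteristic. It is fixed only when T2 is completed, so allocation and what happens during treatment can influence it. In MBT-PP it may reflect rescheduling, slow pace or early stopping as well as slow questionnaire return. Families who take longer may also be families who are doing worse for reasons that the baseline SDQ does not capture.

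If that association differs between arms, the interaction in equation 5.0 picks up the difference in association and not a change of effect with time. The short-interval and long-interval groups are then not comparable across arms, because membership was not determined before randomisation. The SAP does not mention this. It draws the inference in the wrong direction: the analysis exposed to bias is used to question the one that is not. A sound randomised result could be reported with an unwarranted doubt attached, beside subgroup effects that are artefacts.

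**Working it through.** **Inputs from the SAP (Sample size calculations).** 250 families, 1.4 CYP per family, ICC 0.27, R² 0.61 between families and 0.75 within families, allocation 0.50, six level-2 covariates, two-sided alpha 0.05, power 0.80.

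**Reproducing the plan's figure.** The residual variance of a family mean is 0.27 × 0.39 + 0.73 × 0.25 / 1.4 = 0.1053 + 0.1304 = 0.2357, so its SD is 0.485. With df = 250 − 6 − 2 = 242 the multiplier is about 2.81. MDES = 2.81 × 2 × √(0.2357/250) = 0.173; the SAP states 0.17.

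**What the interaction estimates when the effect is constant.** Let ρ be the correlation of weeks with the unmeasured outcome residual, s the SD of weeks and σ the residual SD. The slope on weeks within an arm is ρσ/s, so the expected interaction is

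ρ(MBT)σ/s(MBT) − ρ(TAU)σ/s(TAU).

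It is zero when ρ and s are the same in both arms, or when both correlations are zero.

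**Assumptions not in the documents.** ρ and s are assumed. Two models were simulated with a constant effect of −0.17 SD. Model A ties weeks to the family-level residual only (4,000 trials per scenario, 1.4 CYP per family, family random intercept, minimisation dummies omitted). Model B uses one score per family and ties weeks to the whole family-mean residual (SD 0.485).

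**By hand, Model B, ρ = 0.3 v 0, s = 3 in both arms.** Slope difference = 0.3 × 0.485/3 = 0.0485. SE = √[2 × 0.2357 × (1 − 0.09/2)/(125 × 9)] = 0.0200. The ratio is about 2.4, which exceeds 1.97 in about 67% of trials.

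Share of trials with a significant interaction although the effect is constant:

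| ρ MBT-PP / TAU | SD of weeks MBT-PP / TAU | Model A | Model B |
|---|---|---|---|
| 0 / 0 | 3 / 3 | 5.2% | 5% |
| 0.2 / 0 | 3 / 3 | 17.9% | 34% |
| 0.3 / 0 | 3 / 3 | 34.0% | 67% |
| 0.3 / 0.15 | 3 / 3 | not run | 22% |
| 0.3 / 0.2 | 3 / 3 | not run | 13% |
| 0.3 / 0.3 | 3 / 3 | 4.7% | 5% |
| 0.3 / 0 | 4 / 2 | not run | 33% |
| 0.3 / 0 | 4 / 1 | 8.4% | 13% |

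The two models agree once put on one scale: 0.3 in Model A equals 0.3 × √(0.1053/0.2357) = 0.20 in Model B, and both then give 34%. If weeks depend only on the baseline score, which the model adjusts for, Model A gives 4.7% even at a correlation of 0.5.

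**The split.** With ρ = 0.3 v 0 and equal SDs, Model A gives −0.247 SD below and −0.091 SD above the mean interval. With a true effect of zero it gives −0.077 and +0.075. With SDs of 4 v 1 the interaction is rarely significant, but the split is still distorted (−0.250 and −0.094).

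**The ITT estimate.** In Model A it averaged −0.169 to −0.172 in every scenario with a true effect of −0.17, and −0.001 when the true effect was zero.

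**Weeks as a main effect only.** In Model B the common slope is (0.0485 + 0)/2 = 0.0243 per week. If MBT-PP families average 2 weeks longer, the adjusted effect becomes −0.17 − 2 × 0.0243 = −0.22; at 3 weeks longer it is −0.24.

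**The case against.** The strongest objection is that the asymmetry between arms is plausible but not documented. The SAP's sentence about completing T2 after treatment covers families in both arms. TAU is also paced: the protocol describes guided resources spread over several weeks, and the SAP describes check-ins with a practitioner. Slow replies and rescheduling can occur in either arm. A reader might infer that TAU timing is purely administrative and that the 67% figure is therefore the expected rate. The documents do not support this. The figure needs TAU timing as variable as MBT-PP timing yet unrelated to prognosis; if TAU timing is administrative and tight, the rate is only 8% to 13%. This part of the objection stands and limits what can be said about size.

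The second objection is that this is labelled a sensitivity analysis, the split happens only after a significant interaction, and the ITT model remains primary. That is correct. A reader might infer that the time results replace the ITT estimate, or that the SAP contradicts its own commitment to ITT. Neither follows from the text: it says only that a question would be raised, and an additional model does not deny that ITT best preserves allocation.

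Third, looking at timing is reasonable, since the protocol (Longitudinal follow-ups) expects that effects may need time to embed. A significant interaction could be a real time effect. The planned test cannot tell that from the artefact, which is why it should not carry a verdict on the ITT estimate.

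**Conclusion.** The concern holds as a fault in the inferential rule, not in the primary estimate. The SAP treats an interaction with a variable measured after randomisation as evidence against a randomised comparison, and follows it with subsamples whose boundaries are chosen after seeing the data. A constant effect can produce that signal while the ITT estimate remains unbiased.

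The frequency cannot be stated from the documents. The range of about 18% to 67% rests on assumed correlations of 0.2 to 0.3 in MBT-PP, 0 in TAU and equal interval SDs. It falls to the nominal 5% when the correlations are equal as well, and to 8% to 13% with tight TAU timing. The case for change does not depend on the upper figure: the rule is unsound whenever the link between interval and prognosis may differ by arm, and nothing in the plan excludes that.

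**What to change.** 1. Delete the statement that a significant interaction questions the validity of the ITT estimate.
2. Delete the follow-on analyses in subsamples defined by time.
3. Keep the descriptive summary of T1-T2 weeks by arm.
4. If equation 5.0 is kept, label it exploratory, non-causal, conditioned on a variable measured after randomisation, and unable to overrule the primary result.
5. Do not offer a model with weeks as a main effect as an adjusted estimate of impact. It conditions on the same variable and can move the arm effect, as shown above.
6. Reconcile the SAP's Design overview with its Primary outcome analysis section by stating how T2 was actually timed in each arm. Setting a new T2 clock is not a wording change: the SAP is dated January 2025, already used pilot T2 data, and the protocol schedules efficacy T2 collection for January to April 2025.
7. If the model stays, correct its labels. The text calls both time terms β₅, although equation 5.0 has the main effect as β₄. It also reads a positive interaction as higher impact, although a lower SDQ score is better.

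The cost is SAP wording and the loss of an exploratory look at time.
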